## **7) Procedures Involved**

The study will be conducted in two districts in Hai Duong, a province located near Hanoi, Vietnam. Clusters within both districts will be defined as geographic areas served by local health clinics (commune health stations). In collaboration with commune health stations, community-based screening will be conducted to identify Alzheimer's family caregivers residing in the designated clusters who will then be invited to participate in the study. Clusters will be randomly assigned to either the intervention (approximately 21 clusters, 175 caregivers) or to the enhanced control condition (approximately 21 clusters, 175 caregivers).

Staff from the National Geriatric Hospital and Hai Duong Provincial Hospital will train local staff (e.g., village health workers) to identify persons at high risk for dementia from their caseloads, including those with a history of significant memory problems, behavioral issues and evidence of functional decline.

Research staff from local health clinics will contact potential participants by phone, provide information about the project, and invite them to participate in

**PROTOCOL TITLE: Cluster Randomized Controlled Trial to Test the Efficacy of a Psychosocial Intervention (REACH VN) to Support Alzheimer's Family Caregivers in Vietnam**

screening to determine their eligibility. Verbal consent will be obtained from the older adult and a family member prior to screening by research staff. Those who consent to participate in the screening will undergo an assessment including a brief neurological exam, bedside cognitive testing and dementia stage using standard instruments, including the Mini-Cog, NPI-Q and CDR. Once an older adult has been determined to meet criteria for dementia (i.e, CDR $\geq$ 1), we will identify the adult family member providing the most day-to-day care and invite them to participate in the study and obtain verbal consent. Because of the minimal risk of both screening and behavioral intervention, verbal consent will be obtained for both.

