Study Title: Cluster Randomized Controlled Trial to Test the Efficacy of a Psychosocial Intervention (REACH VN) to Support Alzheimer's Family Caregivers in Vietnam

NCT#: NCT04542317

Document Date: October 15, 2020

Document Type: Statistical Analysis Plan

Statistical Analysis Plan

Intervention and control arms will be compared at baseline on caregiver characteristics, people with ADRD characteristics, and caregiving context using two-sample t-tests for continuous variables and chi-squared tests for categorical variables. The Wilcoxon rank-sum test or Fisher's exact test will be used instead when parametric assumptions are violated. For primary and secondary outcomes, the assessment of intervention effects will be based on intent-to-treat analyses. The 3-month and 6-month assessments will be used as outcomes, while the baseline assessment will be used as a covariate in a mixed-effects regression model. A random intercept for participants nested within communes will be included to account for the correlation among assessments from the same participant, as well as participants belonging to the same commune.

Both unadjusted models and those adjusted for caregiver characteristics (e.g., age, gender, and relationship to people with ADRD) and people with ADRD characteristics (e.g., age, gender, dementia severity, and NPI-Q severity score) will be reported. These covariates are chosen because they are either basic sociodemographic characteristics or variables shown in prior studies to be associated with caregiver psychological stress and burden. Contrasts will be defined to estimate the difference between intervention arms at 3 and 6 months and will be tested using a Wald test. For ease of presentation, primary and secondary outcomes will be z-scored using the baseline mean and standard deviation (SD) in the group. Therefore, differences will be presented in SD units. All analyses will be conducted using SAS software, version 9.4, and a p-value less than 0.025 will be considered significant.

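### Does the primary model leave commune clustering out, or test the arm effect with too many degrees of freedom?

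*SAP*

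**What the plan says.** The Protocol, section 7 (Procedures Involved), makes the commune the unit of allocation: "Clusters will be randomly assigned to either the intervention (approximately 21 clusters, 175 caregivers) or to the enhanced control condition". Section 4 gives a final sample of 350 caregivers and limits clusters to between 5 and 15 participants.

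The SAP fits one mixed-effects regression to each outcome: "The 3-month and 6-month assessments will be used as outcomes, while the baseline assessment will be used as a covariate". The random effects are described in one sentence. It begins "A random intercept for participants nested within communes will be included to account for the correlation among assessments from the same participant" and ends "as well as participants belonging to the same commune".

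On testing, the SAP states: "Contrasts will be defined to estimate the difference between intervention arms at 3 and 6 months and will be tested using a Wald test". It adds "All analyses will be conducted using SAS software, version 9.4" and "a p-value less than 0.025 will be considered significant". It names no SAS procedure, RANDOM statement, denominator degrees-of-freedom method or reference distribution, and does not say whether 0.025 is one- or two-sided. Neither document gives an ICC.

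**The concern.** Two features look wrong for a cluster-randomised trial.

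First, the random intercept is singular and attached to participants within communes. An intercept coded only at that level gives every caregiver an independent effect. It absorbs the correlation between one caregiver's 3-month and 6-month scores, but induces none between two caregivers in the same commune. Because allocation is by commune, the standard error of the arm contrast would then be too small by the square root of the design effect, for every primary and secondary outcome.

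Second, the arm effect is estimated from about 42 communes, which supports about 42 − 2 = 40 degrees of freedom. A Wald test referred to the normal distribution ignores this and gives p-values that are slightly too small.

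If the first problem were real, the false-positive rate could more than double at a moderate ICC. The second is smaller, but it would affect every contrast.

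**Working it through.** **The plan's own figures.** 2 × 175 = 350 caregivers, and 350 / 42 = 8.33 per commune, inside the limits of 5 and 15. The documents give no effect size, SD, ICC or power, so the sample size itself cannot be re-derived.

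**Inputs.** From the documents: about 42 communes, 8.33 caregivers per commune, two outcome times, threshold 0.025. Assumed: two-sided testing, ICC from 0 to 0.10, and within-person correlation of 0.5 or 0.7. The two-sided normal critical value at 0.025 is 2.241.

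**Step 1: commune term left out.** Design effect = 1 + (8.33 − 1) × ICC. True size = 2 × [1 − Φ(2.241 / √design effect)].

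| ICC (assumed) | Design effect | True size |
|---|---|---|
| 0 | 1.000 | 0.025 |
| 0.01 | 1.073 | 0.031 |
| 0.02 | 1.147 | 0.036 |
| 0.05 | 1.367 | 0.055 |
| 0.10 | 1.733 | 0.089 |

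With commune sizes varying between 5 and 15, simulation gives slightly higher values: 0.037, 0.057 and 0.093 at ICC 0.02, 0.05 and 0.10.

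**Step 2: does the SAP leave it out?** Set the two halves of the sentence side by side. The first names participants nested within communes and correlation among one participant's assessments. The second adds correlation among participants who share a commune. A participant-only intercept achieves the first and not the second. Intercepts for commune and for participant within commune achieve both. Only the two-intercept model does what the sentence says it is for, so Step 1 describes a departure from the plan.

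**Step 3: both intercepts present, normal versus t reference.** On 40 degrees of freedom the critical value is 2.329 instead of 2.241. If the statistic follows t with 40 degrees of freedom, P(|t| > 2.241) = 0.0306. If 0.025 is one-sided, the normal critical value is 1.960 and P(t > 1.960) = 0.0285.

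The t formula ignores one feature of the fitted model: the commune variance estimate cannot fall below zero. A simulation of 400,000 null trials per setting allows for this (42 communes of 8 caregivers, two times, contrast at one time, variance components truncated at zero). Ranges cover the two within-person correlations.

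| ICC (assumed) | Normal reference | t reference, 40 df |
|---|---|---|
| 0 | 0.022 | 0.017 |
| 0.01 | 0.024 | 0.019–0.020 |
| 0.02 | 0.026 | 0.021 |
| 0.05 | 0.028 | 0.023 |
| 0.10 | 0.029 | 0.024 |

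The normal reference is closer to 0.025 at ICC 0 to 0.02, and the t reference is closer at 0.05 and above. Neither is far off. A separate simulation with unequal commune sizes gives 0.026, 0.030 and 0.029 for the normal reference, and 0.022, 0.024 and 0.024 for t, at ICC 0.02, 0.05 and 0.10.

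**Step 4: does the SAP choose the normal reference?** It says only that a Wald test will be run in SAS 9.4. A Wald statistic from a SAS mixed model can be referred to t or F, so the normal reference is one possible reading and not a stated choice.

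**The case for a change.** The best case for a change is that a stated purpose does not specify a model. A programmer who coded the singular intercept at participant level could claim to follow the SAP's words, and the SAP offers no code to correct that. The same document plans ordinary two-sample and chi-squared tests for the baseline comparison, with no allowance for communes, so commune-level handling cannot be taken for granted. Leaving the degrees of freedom open also allows the choice to be made after the data are seen. Spelling out both points would take one sentence.

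Part of this stands. The wording is loose, the two intercepts are not written out, and no degrees-of-freedom method is named. The error rates in Step 1 are also correct for the model they describe.

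It does not carry the conclusion. The programmer's claim fails against the second half of the same sentence. The baseline tests are separate from the outcome model, for which commune correlation is named explicitly. With both intercepts in place, the choice between references moves the critical value only from 2.241 to 2.329, so intervals widen by about 4% (2.329 / 2.241 = 1.039). Requiring 40 degrees of freedom in all cases would not be a clear gain either: simulated size falls to 0.017 when the ICC is zero.

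**Conclusion.** The concern does not call for a change. The SAP says that its model accounts for commune clustering, and the singular phrase is shorthand for nested intercepts. Error rates of about 0.036 to 0.093 need both a participant-only coding that contradicts the stated purpose and an assumed ICC of 0.02 to 0.10. Because the model adjusts for each caregiver's baseline score, the relevant ICC is the one that remains after that adjustment, and the documents give no value for it.

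Under the model as its purpose describes it, a normal reference gives a simulated size of 0.022 to 0.030 against a nominal 0.025, with 0.031 as the t-formula figure. A t reference on 40 degrees of freedom gives 0.017 to 0.024. These results assume about 42 communes, two-sided testing, ICC between 0 and 0.10, and no dropout. The unstated degrees-of-freedom method is a gap that an analyst would fill sensibly. It could matter only for a p-value very close to the threshold, since a normal-reference p of 0.025 becomes 0.031 on 40 degrees of freedom.

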## 4) Inclusion and Exclusion Criteria

To be eligible for the cluster RCT, the family member will need to be the identified adult (age 18 and above) primary caregiver (i.e., the person spending who provides the most time day-to-day providing care) to an older adult with dementia who is living in the community. In the event that the primary caregiver

**PROTOCOL TITLE: Cluster Randomized Controlled Trial to Test the Efficacy of a Psychosocial Intervention (REACH VN) to Support Alzheimer's Family Caregivers in Vietnam**

is not available to participate, an alternate family member who providing substantial (i.e., at least 4 hours/day) of care to the older adult with dementia will be eligible. Caregivers will need to score  $\geq 6$  on the Zarit Burden Inventory 4-item version. All participants will be living in designated clusters in Hai Duong, Vietnam. To be eligible, clusters will have a minimum of 5 participants and a maximum of 15 participants. Clusters will be defined as geographic areas serving local health stations.

The final sample for the cluster RCT will be 350 family caregivers of persons diagnosed with dementia (175 in the active intervention and 175 in the control group). The RCT will exclude:

- Caregivers who are unable to consent
- Individuals who are not yet adults (infants, children, teenagers)
- Prisoners

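### The outcome model, as written, pools one variance over 3 and 6 months while each visit is tested separately, so a visit's standard error can be wrong in a direction the documents cannot settle

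*SAP*

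**What the plan says.** The model is set out in the SAP's two paragraphs. On outcomes and baseline: "The 3-month and 6-month assessments will be used as outcomes, while the baseline assessment will be used as a covariate in a mixed-effects regression model". On dependence: "A random intercept for participants nested within communes will be included to account for the correlation among assessments from the same participant", with the same sentence extending to correlation among caregivers, "as well as participants belonging to the same commune". I read this as one intercept for communes and one for participants within communes, so commune clustering is modelled.

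On testing: "Contrasts will be defined to estimate the difference between intervention arms at 3 and 6 months and will be tested using a Wald test", and "a p-value less than 0.025 will be considered significant". The SAP does not mention a residual covariance structure, visit-specific variances, a baseline-by-visit or commune-by-visit term, or a robust standard error.

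Protocol section 2 names psychological distress and caregiver burden as primary outcomes. Section 6 describes an intervention of up to 3 months with follow-up at 3 and 6 months. Sections 4 and 7 give 350 caregivers, about 21 communes per arm and 5 to 15 caregivers per commune.

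**The concern.** A random-intercept model coded literally, with the default residual, carries two restrictions: the variance left after baseline is equal at 3 and 6 months, and a commune's shared effect is identical at both. If baseline enters as a single covariate, one baseline slope also serves both visits.

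These restrictions would matter little for an arm effect averaged over the visits. Here each visit has its own test, and with complete data both tests use the same pooled standard error. If the visits differ in variance, one test rejects too often under the null and the other is conservative and loses power. A commune-level shift specific to one visit has no term in the model. The same model serves both primary outcomes.

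**Working it through.** **What can be reproduced.** The 350 cannot be rebuilt, because no power, effect size, SD, ICC or dropout is stated. The only available check is 175/21 = 8.33 caregivers per commune, which lies inside the limits of 5 and 15.

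**Inputs from the documents.** k = 21 communes per arm, m = 8.33, nominal level 0.025.

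**Assumptions.** Two-sided test (sidedness is not stated), so the critical value is z = 2.241. Normal reference, complete data, equal commune sizes. Outcome variance 1 at each visit, split into commune variance τ² = 0.05 (ICC 0.05) and individual variance 0.95. Baseline correlation r at visit v leaves σ_v² = 0.95(1 − r_v²).

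**Formulas.** The true variance of the arm contrast at visit v is (2/k)·V_v, with V_v = τ_v² + σ_v²/m. A visit's contrast is the two-visit average plus or minus half the between-visit difference. The random-intercept model treats those two parts as uncorrelated, and it divides any commune-level difference by m as if it were individual noise. With a constant commune effect its variance is therefore (2/k)·(V_3 + V_6)/2 at both visits. Actual error is 2[1 − Φ(2.241 × model SE / true SE)].

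**A. Unequal adjusted variance, constant commune effect.**

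- r = 0.7 then 0.5. σ² = 0.4845 and 0.7125, so V_3 = 0.05 + 0.0581 = 0.1081 and V_6 = 0.05 + 0.0855 = 0.1355, mean 0.1218. True SEs are √(0.1081 × 2/21) = 0.101 and 0.114, and the model SE is 0.108 at both. The ratios of 1.061 and 0.948 give error 0.017 at 3 months and 0.034 at 6. Simulation of 8,000 null trials with commune sizes 5 to 15 and a t reference gave the same three SEs and error 0.016 and 0.031.
- r = 0.6 then 0.5. V = 0.1230 and 0.1355, mean 0.1292. Ratios 1.025 and 0.977, error 0.022 and 0.029.
- Equal r. Ratio 1.000 at both visits, error 0.025 and 0.025.

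**B. Reversal.** Scale the adjusted SD at 6 months to 0.9 of its 3-month value, with the ICC of the adjusted outcome at 0.03. Relative variances are 1 and 0.81, mean 0.905. Ratios are √0.905 = 0.951 at 3 months and √(0.905/0.81) = 1.057 at 6, so error is 0.033 at 3 months and 0.018 at 6.

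**C. Equal variances, commune effects correlated 0.5 between visits.** Take τ² = 0.05 and σ² = 0.95 on the adjusted scale. True V = 0.05 + 0.95/8.33 = 0.164. The commune average has variance 0.05 × 1.5/2 = 0.0375 and the half-difference 0.05 × 0.5/2 = 0.0125. The model's value is 0.0375 + 0.114 + 0.0125/8.33 = 0.153. The ratio √(0.153/0.164) = 0.966 gives error 0.030 at both visits. For ICC 0.02 to 0.10 the error is 0.027 to 0.034.

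**D. Both departures.** r = 0.7 then 0.5 with commune correlation 0.5 gives error 0.023 at 3 months and 0.043 at 6. The commune shift cancels most of the 3-month conservatism seen in A.

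**Effect of visit-specific variances.** In the simulated settings with unequal correlations or shifting commune effects, a model with visit-specific terms held error at 0.023 to 0.026. When the visits were alike, both models gave 0.025 to 0.026 with SE 0.108.

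**The case against.** The tempting stronger reading is that the 6-month standard error is likely too small and the 3-month one too large, because correlation with baseline tends to weaken over time. The documents do not support that. They give no variance, ICC or correlation at any visit, and decaying correlation is not enough without stable total variance. Ignoring clustering, r = 0.6 then 0.5 leaves 0.64 and 0.75. A total SD about 8% lower at 6 months (√(0.64/0.75) = 0.924) removes the difference, and a larger fall reverses it. Such a fall is not excluded: the 3-month visit comes at the end of an intervention that varies from 3 to 6 sessions (Protocol section 7), so responses could be most mixed then. Nor do the two restrictions act together at 3 months, as C and D show. This part of the objection stands, and the direction must stay conditional.

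It is also fair that the SAP does not explicitly adopt equal variances. It is silent on the residual and does not rule out a baseline interaction. Two-level random intercepts are a conventional choice, and the larger figures need assumptions nobody can verify from these documents. A commune-by-visit variance from about 42 small communes would be imprecise, and a rule to drop it if estimated at zero would make the model depend on the data.

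What does not stand is that this is only missing detail. The sentence coded literally gives the restrictive model. In every departure examined, at least one visit's test exceeded 0.025, and the better model lost nothing in simulation when it was not needed.

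**Conclusion.** The point holds in conditional form. With the usual residual, the planned model gives both visits one pooled variance and a time-constant commune effect, although the inference is visit by visit. If adjusted variances differ, the more variable visit gets too small a standard error and the other too large. If commune effects shift, the standard error tends to be too small, and at both visits when variances are equal.

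The size is modest: standard errors off by about 2 to 6% in cases A to C, and actual error of roughly 0.017 to 0.034 against 0.025. It reaches about 0.043 only when both departures are assumed together. These figures rest on assumed ICCs and correlations, complete data and a normal reference. Degrees of freedom are a separate matter not counted here. The change is worth making because it is nearly free and affects both primary outcomes. It does not call the design into question.

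**What to change.** Before unmasked analysis, amend the model sentence in the SAP:

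- Keep the commune random intercept. Replace the participant intercept with an unstructured 2×2 residual covariance across visits (in PROC MIXED, REPEATED visit / SUBJECT=participant(commune) TYPE=UN).
- Add baseline-by-visit, and take both the 3- and 6-month contrasts from this model.
- Pre-specify a sensitivity analysis that adds a commune-by-visit random term, reported whatever its estimated variance, with no data-dependent drop rule. The main model still holds the commune effect constant over time, so this analysis is what would reveal a commune shift.

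The cost is about two extra parameters: three covariance parameters in place of the participant and residual variances, plus one more baseline slope. The interval becomes slightly wider at whichever visit is more variable and slightly narrower at the other. Nothing changes in design, sample size or data collection.

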## 2) Objectives

The objective of this study is to conduct a cluster randomized controlled trial to test the efficacy of a psychosocial intervention to support Alzheimer's family caregivers in Vietnam. The cluster RCT will test the hypothesis that family caregivers who receive the intervention will show lower psychological distress and lower caregiver burden compared with those in the control group (primary outcomes). In addition, we will conduct secondary analyses to examine whether intervention group has lower perceived stress and somatic symptoms.

Exploratory analyses will be conducted to determine if intervention effects are mediated by caregiver self-efficacy or knowledge gain.

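### Does z-scoring by the baseline mean and SD of an undefined group put the primary test at risk?

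*SAP*

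**What the plan says.** The scaling rule is in the second paragraph of the SAP: "primary and secondary outcomes will be z-scored using the baseline mean and standard deviation (SD) in the group". The sentence opens by giving ease of presentation as the reason, and the next one draws the consequence: "Therefore, differences will be presented in SD units".

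The model is described in the first paragraph. The 3- and 6-month assessments are the outcomes, "while the baseline assessment will be used as a covariate in a mixed-effects regression model", with random intercepts for participants nested within communes. The tests are given just before the scaling rule: "Contrasts will be defined to estimate the difference between intervention arms at 3 and 6 months and will be tested using a Wald test". The threshold closes the paragraph: "a p-value less than 0.025 will be considered significant".

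The SAP uses the word *group* only in the scaling rule. It does not define the word, and it does not say whether scaling comes before or after model fitting, or whether the baseline covariate is scaled too. The Protocol has no analysis section that would settle these points.

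**The concern.** The Protocol uses *group* for a randomised arm. Section 2 has "compared with those in the control group (primary outcomes" and "whether intervention group has lower perceived stress and somatic symptoms"; Section 4 has "175 in the active intervention and 175 in the control group". A reader who carries that usage into the SAP could standardise each arm by its own baseline mean and SD.

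Done before modelling, that would change the test. Each arm's baseline mean would be set to zero, so the baseline covariate would carry no information about chance imbalance between arms. The arm contrast would become a difference in change scores, while the model would still report the smaller standard error of a covariate-adjusted comparison. The two arms would also be on slightly different scales. The rule covers both primary outcomes at both time points, so the trial's main p-values would be anti-conservative.

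**Working it through.** **Inputs.** From the documents: threshold 0.025 (SAP); 175 caregivers per arm (Protocol Section 4); about 21 clusters per arm (Protocol Section 7); baseline as covariate, with participant and commune random intercepts (SAP). Assumed, because the documents do not give them: a two-sided test (critical z = 2.2414), a baseline to follow-up correlation r of 0.3 to 0.7, and an ICC of 0.02 to 0.05. The 0.025 is a chosen threshold with no derivation, so the plan has no figure of its own to reproduce here.

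**Step 1: one common reference.** Let Y* = (Y − m)/s and X* = (X − m)/s, with the same m and s for everyone. The arm coefficient becomes β/s and its standard error SE/s, so the Wald ratio is (β/s)/(SE/s) = β/SE, as on the raw scale. This holds whether m and s come from the whole sample or from the control arm. It also holds if the baseline covariate is left raw, since only the intercept and slope then change. If scaling is applied after fitting, the test is the raw-score test by construction.

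**Step 2: own-arm reference for both outcome and baseline, before fitting.** Write D_Y and D_X for the arm differences in mean follow-up and mean baseline, with unit variances.

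- Own-arm centring makes the contrast D_Y − D_X, with variance proportional to 2(1 − r).
- The model reports a variance proportional to 1 − r².
- The ratio of true to reported variance is 2(1 − r)/(1 − r²) = 2/(1 + r).
- Type I error = 2·[1 − Φ(2.2414/√(2/(1 + r)))].

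| r | √(2/(1+r)) | Type I error |
|---|---|---|
| 0.3 | 1.24 | 0.071 |
| 0.5 | 1.15 | 0.052 |
| 0.7 | 1.08 | 0.039 |

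**Step 3: simulation of the SAP model under the null.** Settings: 42 communes, about 350 caregivers, two follow-ups, both random intercepts, REML, 5,000 replicates per setting, normal critical values, and no common change over time.

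| r | ICC | Own arm | Pooled |
|---|---|---|---|
| 0.3 | 0.02 | 0.069 | 0.026 |
| 0.5 | 0.02 | 0.056 | 0.031 |
| 0.7 | 0.02 | 0.041 | 0.027 |
| 0.3 | 0.05 | 0.074 | 0.026 |
| 0.5 | 0.05 | 0.060 | 0.030 |
| 0.7 | 0.05 | 0.047 | 0.029 |

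With t on 40 degrees of freedom, the own-arm rates in these settings fall to 0.034–0.064 and the pooled rates to 0.021–0.025.

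**Step 4: size on the estimate.** At 175 per arm, ignoring clustering, a one-standard-error chance baseline difference is √(2/175) = 0.107 SD. Own-arm scaling moves the contrast by (1 − r) × 0.107, which is 0.075, 0.053 or 0.032 SD at r = 0.3, 0.5 or 0.7. Randomisation makes the expected imbalance zero, so the null estimate is not systematically biased. The fault would lie in the standard error and the p-value.

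**Step 5: which reading the text supports.**

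- The SAP says *arms* both times it names the randomised groups, for the baseline comparison and for the contrasts. It then changes to a singular *group*. An own-arm rule would naturally have said *each arm*.
- The stated purpose is presentation, which is no reason to alter the test.
- The stated result is a between-arm difference in SD units. Two arms divided by two different SDs have no common unit, so own-arm scaling defeats the sentence that follows it.
- In Sections 2 and 4 of the Protocol, wherever *group* means an arm it carries a qualifier (control, intervention). The SAP's bare use does not match that pattern.

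**The case for a change.** The strongest reply is that a SAP should let two analysts reach the same p-value, and that this sentence, taken alone, does not. The own-arm figures are also not a ceiling. With a common fall of 1 SD in both arms (r = 0.5, ICC 0.05), the simulated rate is 0.105.

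The SAP also separates the outcomes from the baseline covariate, so a literal analyst might scale the outcome by arm and leave baseline raw. The contrast is then D_Y − (1 + r)D_X, the variance ratio is (2 − r²)/(1 − r²), and the closed-form type I error is about 0.12, 0.14 and 0.19 at r = 0.3, 0.5 and 0.7. Closing off these readings would cost one phrase.

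The arithmetic stands, and so does the observation that the term is undefined. What does not stand is the step from an undefined word to an error-rate defect. Every inflated figure requires own-arm scaling applied before the fit, and no sentence in either document states either condition. The support for own-arm scaling is borrowed from another document's vocabulary and conflicts with the SAP's own next sentence.

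**Conclusion.** No change to the plan follows. This is a gap in wording that an analyst would fill sensibly from the surrounding text. The natural reading is one common baseline mean and SD used to express results in SD units. Under it the Wald test is identical to the raw-score test and nothing is lost; the control-arm reading gives the same result.

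The inflation, about 0.04 to 0.07 against a nominal 0.025 for r from 0.7 to 0.3, arises only if outcome and baseline are both z-scored by own arm before fitting. It would be larger with a common shift over time or with a raw baseline covariate. These figures rest on assumed correlations and ICCs and on a two-sided test. They illustrate a procedure that the SAP does not describe and are not an estimate of this trial's error rate.
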